7.6 Treatment Compliance

Study intervention compliance will be monitored as indicated in the Schedule of Activities using standard study intervention accountability procedures (comparing the number of tablets returned to number dispensed, considering the expected regimen, and reported missed doses). Study intervention accountability will be reviewed by the investigative site staff at each visit to assess treatment compliance. Site staff will discuss any discrepancies with the participant and remind the participant of the importance of compliance with the assigned regimen.

7.7 Concomitant Therapy

All prior treatments for AA should be recorded on the electronic Case Report Form (eCRF).

All medications taken within 4 weeks of the first dose of study intervention on Day 1 through the Post-Treatment Follow-up visit should be recorded on the eCRF.

Concomitant medications (prescription, over the counter, or herbal) should be administered during the study only if they are to be used for treatment of specific medical reasons.

A non-live vaccine may be administered during the study, but the effect on immune responses with study intervention is unknown and could be blunted (see Section 7.7.2).

Use of systemic corticosteroid medications (< 7 days in duration) to treat non-AA medical conditions is allowed but should be discussed with the Medical Monitor to determine if the intercurrent condition affects the safety of the participant, or if the corticosteroid treatment is likely to confound efficacy assessments.

Note: Topical corticosteroids and topical calcineurin inhibitors are permitted but cannot be applied on the eyelids, eyebrows, or scalp. Otic, ophthalmic, nasal, and inhaled corticosteroids within recommended doses and with no systemic effects are permitted.

7.7.1 Prohibited and/or Restricted Treatments

Prohibited and/or restricted medications during the study are described below. Refer to Section 6.2 Exclusion Criteria-Previous/Concomitant Therapy for medical restrictions affecting eligibility.

- Use of any medications/therapy that would affect hair regrowth
- Any use of biologic medications (eg, adalimumab, etanercept, infliximab, ustekinumab)
- Any use of JAK inhibitors (eg, tofacitinib, baricitinib, ritlecitinib).
- Live vaccination (including, but not limited to, any live attenuated COVID-19 vaccines) should not be used during the study, including the safety follow-up period of 30 days following last dose of IP (see Section 7.7.2 for permitted vaccines).
- Exposure to any investigational drug, investigational vaccine, or placebo outside of the current study. Specifically, participants currently in other interventional trials for COVID-19, including investigational COVID-19 vaccination trials that are not authorized or approved by relevant health authorities, should not participate in BMS clinical trials.

7.7.2 Permitted Vaccines (Including COVID-19 Vaccine)

Administration of a non-live vaccine is allowed during the study. However, the efficacy and safety of non-live vaccines (including non-live COVID-19 vaccines) in participants receiving deucravacitinib is unknown. The following are examples of non-live vaccines: inactivated vaccines (eg, heat-killed and formalin-killed vaccines); subunit vaccines (eg, influenza and pneumococcal vaccines); toxoid vaccines; nucleic acid vaccines that do not encode potentially infectious virus: messenger mRNA vaccines (eg, Comirnaty, Pfizer/BioNTech; Spikevax, Moderna COVID-19 vaccines), and replication-incompetent recombinant adenovirus vector DNA vaccines (eg, Vaxzevria, AstraZeneca/University of Oxford COVID-19 vaccine).

For COVID-19 vaccines, the full series per local guidance should be completed prior to enrollment when feasible and when a delay in enrollment would not put the study participant at risk. Ideally, AEs attributable to a vaccine should have resolved prior to enrollment.

If a participant has received a specific COVID-19 vaccination, details such as type and date of vaccine received should be recorded on the COVID-19 Vaccination Form.

Please contact the Medical Monitor with any questions related to COVID-19 vaccines.

7.8 Continued Access to Study Intervention After the End of the Study

At the end of the study, BMS will not continue to provide BMS-supplied study intervention to participants/investigators unless BMS chooses to extend the study. The investigator should ensure that participants continue to receive appropriate standard of care to treat AA.

BMS reserves the right to terminate access to BMS-supplied study intervention if for example but not limited to the following: a) the study is terminated due to safety concerns; b) the development of deucravacitinib for AA is terminated for other reasons, including but not limited to, lack of efficacy and/or not meeting the study objectives; c) the participant can obtain medication from a government-sponsored or private health program. In all cases, BMS will follow local regulations.

8 DISCONTINUATION CRITERIA

8.1 Discontinuation from Study Intervention

Participants MUST discontinue IP (and Non-IP/AxMP at the discretion of the investigator) for any of the following reasons:

- Participant's request to stop study intervention. Participants who request to discontinue study
 intervention will remain in the study and must continue to be followed for protocol-specified
 follow-up procedures. The only exception to this is when a participant specifically withdraws
 consent for any further contact with him/her or persons previously authorized by the participant
 to provide this information
- Any clinical AE, laboratory abnormality, or intercurrent illness which, in the opinion of the investigator, indicates that continued participation in the study is not in the best interest of the participant
- Termination of the study by BMS
- Loss of ability to freely provide consent through imprisonment or involuntarily incarceration for treatment of either a psychiatric or physical (eg, infectious disease) illness. (Note: Under specific circumstances and only in countries where local regulations permit, a participant who has been imprisoned may be permitted to continue as a participant. Strict conditions apply, and BMS approval is required)
- Participant reports suicidal ideation, suicidal behavior, or suicide attempts at any time after randomization. The participant should then be immediately referred to a mental health professional for evaluation of suicide risk
- Abnormal liver tests suggestive of drug-induced liver injury (DILI), or if the investigator believes that it is in the best interest of the participant
- Malignancy; however, a participant who develops non-melanoma skin cancer may continue in the study at the discretion of the investigator
- Pregnancy, positive pregnancy test, or participant expresses an interest in becoming pregnant
- Participant develops active TB during the study or prematurely discontinues treatment for LTBI, or participant is noncompliant with LTBI therapy
- Japan only: Participant with positive HBsAb at Screening or positive HBcAb with negative or undetectable HBV DNA (< 1.3 Log IU/mL [20 IU/mL]) at Screening, for whom quantitative

45

Protocol Amendment No.: 02 Date: 29-Aug-2023

HBV DNA becomes detectable ($\geq 1.3~Log~IU/mL$ ([20 IU/mL]) at any time during treatment with the IP

- Inability or failure to comply with protocol requirements, in the opinion of the investigator
- Unblinding of a participant's study intervention assignment, to investigator or participant, for any reason (emergency or nonemergency)

Refer to the Schedule of Activities for data to be collected at the time of treatment discontinuation and follow-up and for any further evaluations that can be completed.

All participants who discontinue study intervention should comply with protocol-specified follow-up procedures as outlined in Section 2 (Table 2-3). The only exceptions to this requirement is when a participant withdraws consent for all study procedures, including post-treatment study follow-up, or loses the ability to consent freely (eg, is imprisoned or involuntarily incarcerated for the treatment of either a psychiatric or physical illness).

If study intervention is discontinued prior to the participant's completion of the study, the reason for the discontinuation must be documented in the participant's medical records per local regulatory requirements in each region/country and entered on the appropriate Case Report Form (CRF) page.

8.1.1 Temporary Interruption

Temporary study intervention interruption is only allowed if the participant develops an AE that, in the opinion of the investigator, indicates that it is in the participant's best interest that the study intervention be interrupted.

Study intervention in this situation should be stopped until the AE has resolved per investigator judgment.

Temporary interruption of study intervention should be implemented in the context of clinical suspicion for SARS-CoV-2 infection or a positive diagnostic test for SARS-CoV-2. When study intervention is interrupted in a confirmed case of SARS-CoV-2 infection, the investigator should determine whether the resolution of symptoms alone (ie, without repeat diagnostic testing for SARS-CoV-2) is sufficient to resume study intervention. The investigator may consult with the Medical Monitor.

Temporary interruption of study intervention may be considered in the event of SARS-CoV-2 vaccination according to local guidelines.

Any temporary study intervention interruption, as well as restart, must be documented on the appropriate CRF page.

8.1.2 Post-study Intervention Study Follow-up

Participants who discontinue study intervention may continue to be followed.

Participants who discontinue study intervention should complete all assessments indicated for the Week 52/Early Discontinuation (ED) visit and the Post-treatment Follow-up visit as outlined in the Schedule of Activities (Table 2-3).

Protocol Amendment No.: 02

Date: 29-Aug-2023 46

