HBV DNA Test (Japan only)	X	X	Testing will occur every 4 or 8 weeks (frequency of testing is positive HBsAg, but the discretion of the investigator)			positive HBcAb and/or HBsAb result at Screening.	

Table 2-3: On Treatment (Week 28 through Week 52) and Post-Treatment Follow-Up (Week 56) Procedural Outline (IM011134)

Procedure	Week 28 (D197±3 d)	Week 32 (D225±3 d)	Week 40 (D281± 7 d)	Week 48 (D337±7d)	Week 52/ED ^a (D365 ± 3 d)	Week 56/Post- Treatment Follow-Up (D393 ± 3 d)	Notes
Study Intervention							
Dispense Study Intervention	X	X	X	X			Dispense study intervention after all visit procedures have been performed.
Assess Study Intervention Compliance/ Perform Study Intervention Reconciliation	X	X	X	X	X		
Abbreviations: AA-IGA, Alopecia Ar							verse event;
D, I antibody; HBsAb, hepatitis B surface potential.		IBsAg, hepatit	is B surface	antigen; HBV	, hepatitis B vir	us;	on; HBcAb, hepatitis B core OCBP, women of childbearing

^a ED: For participants who discontinue from the study prior to Week 52, all assessments scheduled for Week 52 are to be performed.

b Photography of the scalp is required.

Photography of eyebrows and eyelashes is optional and will only be performed on participants who provide consent. In those who consent, if new onset of eyebrows and/or eyelashes involvement (that is not involved at baseline) is observed after Week 24, a photograph should be taken at the visit when first observed, in addition to Weeks 40 and 52.

d If the urine pregnancy is positive, a serum pregnancy test should be performed to confirm urine test results prior to discontinuing the participant. Study intervention is not to be administered until the results of the confirmatory test are known and negative.

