8.2 Discontinuation from the Study

Participants who request to discontinue study intervention should remain in the study and may continue to be followed for protocol-specified follow-up procedures. The only exception to this is when a participant specifically withdraws consent for any further contact with him/her or persons previously authorized by participant to provide this information.

- Participants should notify the investigator of the decision to withdraw consent from future follow-up.
- The withdrawal of consent should be explained in detail in the medical records by the investigator, as to whether the withdrawal is from further treatment with study intervention only or also from study procedures and/or post-treatment study follow-up, and entered on the appropriate CRF page.
- In the event that vital status (whether the participant is alive or dead) is being measured, publicly available information should be used to determine vital status only as appropriately directed in accordance with local law.
- If the participant withdraws consent for disclosure of future information, the Sponsor may retain and continue to use any data collected before such a withdrawal of consent.

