8.2.1 Individual Discontinuation Criteria

- A participant may withdraw completely from the study at any time at his/her own request, or may be withdrawn at any time at the discretion of the investigator for safety, behavioral, compliance, or administrative reasons. This is expected to be uncommon. Stopping study intervention is not considered withdrawal from the study.
- At the time of discontinuing from the study, if possible, an early termination visit should be conducted, as shown in the Schedule of Activities. See the Schedule of Activities for data to be collected at the time of study discontinuation and follow-up and for any further evaluations that need to be completed.
- The participant will be permanently discontinued both from the study intervention and from the study at that time.
- If the participant withdraws consent for disclosure of future information, the Sponsor may retain and continue to use any data collected before such a withdrawal of consent.

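### The follow-up rules after stopping study drug conflict, and the visits they name omit Week 24, so an obtainable primary SALT value can go uncollected

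*Combined protocol and SAP*

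**What the plan says.** **Endpoint and analysis.** Table 4-1 puts the primary endpoint (change in SALT) and all three secondary efficacy endpoints at Week 24. Section 10.4.1 analyses all randomized participants by assigned arm. Section 10.4.2 handles missing primary values by multiple imputation under missing at random. Details and sensitivity analyses are left to a SAP that is not in the supplied text.

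**Drug versus study.** Section 8.2.1: "Stopping study intervention is not considered withdrawal from the study".

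**Follow-up after stopping drug.**
- Section 8.1, participants who ask to stop: they "will remain in the study and must continue to be followed for protocol-specified" follow-up procedures.
- Section 8.2, the same group: they "should remain in the study and may continue to be followed for protocol-specified follow-up procedures".
- Section 8.1, everyone who stops: "All participants who discontinue study intervention should comply with protocol-specified follow-up procedures as outlined in Section 2 (Table 2-3"). It calls this a requirement and allows only two exceptions: withdrawal of consent for all procedures, or loss of the ability to consent freely. It also says, more generally, "Refer to the Schedule of Activities for data to be collected at the time of treatment discontinuation and follow-up and for any further evaluations", where the wording is permissive and no visit is named.
- Section 8.1.2, everyone who stops: "Participants who discontinue study intervention may continue to be followed", and then "Participants who discontinue study intervention should complete all assessments indicated for the Week 52/Early Discontinuation (ED) visit and the Post-treatment Follow-up visit".

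**Early discontinuation (ED) visit.** Table 2-3, footnote a: "For participants who discontinue from the study prior to Week 52, all assessments scheduled for Week 52 are to be performed". There the trigger is leaving the study; in Section 8.1.2 it is stopping drug.

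**Week 24 lock.** Sections 5.1 and 10.4.1 let the lock proceed once each participant has reached or completed Week 24 or has discontinued before it. Neither says whether that means drug or study.

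**The concern.** A participant who stops drug at, say, Week 8 and stays in the study belongs to the primary analysis, and the Week 24 SALT can be measured. The text a site would consult when drug is stopped names a table beginning at Week 28 and two visits, ED and Post-treatment Follow-up. The Week 24 SALT is scheduled in Table 2-2, which the discontinuation text does not cite by number.

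If the visit is skipped, an obtainable value is replaced by imputation under an assumption the trial's data cannot test. The three secondary endpoints lose the same visit. A SAP can decide how to handle the gap but cannot recover an assessment that was never made. The undefined lock term adds to this: if it is read as stopping drug, the lock need not wait for these participants to reach Week 24.

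**Working it through.** **1. The visits named for a participant off drug, against the primary time point**

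| Source | What it names | Includes Week 24 (Day 169 ± 3)? |
|---|---|---|
| Section 8.1, participant request | Follow-up procedures, no visits listed | Not stated |
| Section 8.1, all who stop | Table 2-3: Weeks 28, 32, 40, 48, 52/ED, 56 | No |
| Section 8.1, general pointer | Schedule of Activities as a whole | By inference only |
| Section 8.1.2 | Week 52/ED and Post-treatment Follow-up | No |
| Section 8.2 | Follow-up procedures, no visits listed | Not stated |

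Even a site that holds every Table 2-3 visit has its first fixed-date SALT at Day 197, which is 197 − 169 = 28 days after the primary time point.

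**2. Strength of obligation**

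For participants who ask to stop, Section 8.1 says *must* and Section 8.2 says *may*. For everyone who stops, Section 8.1 says *should*, with limited exceptions, and Section 8.1.2 says *may*. These cannot all be the operative rule.

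**3. The plan's own power figures**

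Inputs from Section 10.2: difference 39, SD 43, 30 per arm, 15% dropout. The plan tabulates 25 per arm (30 × 0.85 = 25.5).

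- Standard error of a difference = 43 × √(2/25) = 12.16 points.
- Two-sided noncentral t, 25 per arm: 93.5% at alpha 0.10 and 88.1% at alpha 0.05.
- Stated: 93% and 88%. Both reproduce.

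The plan already allows for 15% loss, so the issue is the as-assigned estimate and not the stated power.

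**4. A bound on the bias (hypothetical)**

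Let *p* be the share of an active arm that stops drug, stays in the study and has no Week 24 SALT. Let *k* be the share of benefit kept off drug at Week 24. Suppose imputation credits these participants with the full 39 points.

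- As-assigned difference = 39 × [1 − *p*(1 − *k*)]
- Overstatement = 39 × *p* × (1 − *k*)

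| *p* (assumed) | Participants of 30 | *k* = 1 | *k* = 0.5 | *k* = 0 | *k* = 0 as a share of 12.16 |
|---|---|---|---|---|---|
| 5% | 1.5 | 0 | 0.98 | 1.95 | 0.16 |
| 10% | 3 | 0 | 1.95 | 3.90 | 0.32 |
| 15% | 4.5 | 0 | 2.93 | 5.85 | 0.48 |

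The documents give neither *p* nor *k*. The 15% in Section 10.2 is a dropout allowance; it is neither an estimate of *p* nor a ceiling on it.

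**The case against.** The best opposing case is that the protocol, read as a whole, expects participants off drug to keep attending. Section 8.1 limits the exceptions to follow-up, Section 8.2.1 separates stopping drug from withdrawal, and Appendix 9 says Japanese participants taken off drug for detectable HBV DNA should continue in the study as Section 8.1 describes. Section 8.1 also refers to the Schedule of Activities generally. All of this stands. It supports inferring a Week 24 visit, but none of it names one, and Section 8.1.2 is more specific and more permissive.

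A reader might go further in several ways that the documents do not support:

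- **That the on-treatment title of Table 2-2 excludes participants off drug.** Table 2-3 carries the same label for Weeks 28 to 52, yet Section 8.1 sends those participants to it.
- **That the ED or follow-up SALT would almost never fall at Week 24, or that medication recording (Section 7.7) would usually end before it.** Both need the ED visit on the stop day and follow-up 28 days later. The protocol never states that timing for early stoppers; Table 2-3 dates the follow-up visit at Day 393.
- **That 5.9 points is an expected bias.** It needs 15% of an arm to stop but stay, no retained benefit, and imputation that restores the whole effect. SALT is scheduled every 4 weeks to Week 24, and a model using post-stop values need not restore it.
- **That the SAP mishandles off-drug values.** It was not supplied, so this cannot be judged.

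There is also doubt about the text itself. The Table 2-2 abbreviation list defines ED, although ED appears nowhere else in the visible table, and footnote a is cut off. The Amendment 01 summary in Appendix 10 describes that footnote as concerning Week 0 assessments before dosing, but it describes an earlier amendment. A removed note on early discontinuation is possible.

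**Conclusion.** The point holds as a conflict in the discontinuation text with a specific consequence. The table and visits named for participants off drug leave out the time point of the primary and all secondary efficacy endpoints. A site following Section 8.1.2 can therefore leave an obtainable Week 24 SALT to imputation. The documents do not show that sites are told to skip the visit or that most would.

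The size is unknown. The range of 0 to 5.9 points is a hypothetical bound resting on the assumed shares and full-effect imputation above; its top is 0.48 of one standard error. In a 90-participant Phase 2 study meant to give a preliminary picture (Section 5.4), that would not by itself overturn a 39-point effect. The correction is still worth making because the loss is avoidable and cannot be repaired later. Confidence is medium, given the possible removed note in Table 2-2.

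**What to change.** - Reconcile Sections 8.1, 8.1.2 and 8.2 and Table 2-3 footnote a, so that one rule states who is followed after stopping drug and what triggers the ED visit.
- State that every participant who has not withdrawn from the study, on or off drug, has SALT and AA-IGA at Week 24 (Day 169), with any other hair-loss therapy recorded up to that visit. Keep the existing ED and follow-up assessments as well.
- Define the lock in Sections 5.1 and 10.4.1 as all participants having reached Week 24 or withdrawn from the study.
- Confirm in the SAP that observed off-drug Week 24 values are used in the as-randomized analysis.

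The cost is protocol wording plus one brief, non-invasive visit for each participant who stops early and stays: 1.5 to 4.5 per arm at the assumed 5% to 15%. No drug rule changes and no extra participants are needed. The lock comes no later than if these participants had remained on drug. The estimated effect may be slightly smaller. Participants who withdraw consent or are lost to follow-up remain missing under any wording.

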8.2 Discontinuation from the Study

Participants who request to discontinue study intervention should remain in the study and may continue to be followed for protocol-specified follow-up procedures. The only exception to this is when a participant specifically withdraws consent for any further contact with him/her or persons previously authorized by participant to provide this information.

- Participants should notify the investigator of the decision to withdraw consent from future follow-up.
- The withdrawal of consent should be explained in detail in the medical records by the investigator, as to whether the withdrawal is from further treatment with study intervention only or also from study procedures and/or post-treatment study follow-up, and entered on the appropriate CRF page.
- In the event that vital status (whether the participant is alive or dead) is being measured, publicly available information should be used to determine vital status only as appropriately directed in accordance with local law.
- If the participant withdraws consent for disclosure of future information, the Sponsor may retain and continue to use any data collected before such a withdrawal of consent.

